6.1. Inclusion Criteria

Patients are eligible to be included in the study only if they meet all of the following criteria at screening:

Type of Patient and Disease Characteristics

- [1] Have been diagnosed with T2DM based on the World Health Organization classification or other locally applicable diagnostic standards

Patient Characteristics

- [2] Have HbA1c between $\geq 7.5\%$ (58 mmol/mol) and $\leq 10.5\%$ (91 mmol/mol) at screening as determined by the central laboratory at Visit 1
- [3] On stable treatment with unchanged dose of at least 1 and no more than 3 oral antihyperglycemic drugs, which may only include metformin, SGLT-2i, and/or sulfonylurea for at least 3 months before Visit 1
- [4] Increased risk of CV events as defined by at least 1 of the following (a – e):
 - a) Coronary heart disease documented as having any of the following:
 - 1) History of acute myocardial infarction (ST elevation or non-ST elevation)
 - 2) Stenosis of $\geq 50\%$ in at least 1 major (left main, left anterior descending, ramus intermedius, left circumflex, right) coronary artery as determined by cardiac imaging
 - 3) Coronary calcium score ≥ 300
 - 4) Stable angina pectoris treated with anti-anginal medication
 - 5) Asymptomatic cardiac ischemia documented by cardiac imaging on exercise or pharmacological stress test
 - 6) History of coronary revascularization (percutaneous coronary intervention or coronary artery bypass surgery)

OR

- b) Peripheral arterial disease presumed to be of atherosclerotic origin documented as a history of any of the following:
 - 1) Current or intermittent claudication
 - 2) Resting limb ischemia
 - 3) Stenosis of $>50\%$ in an iliac, femoral, popliteal, or subclavian artery
 - 4) An ankle-brachial index ≤ 0.90
 - 5) Peripheral arterial revascularization or amputation due to atherosclerotic vascular disease
 - 6) Asymptomatic carotid artery stenosis $\geq 70\%$
 - 7) Carotid artery revascularization

8) Abdominal aortic aneurysm

OR

- c) Cerebrovascular disease presumed to be of atherosclerotic origin documented as a history of ischemic stroke or transient ischemic attack (TIA). Patients with a history of TIA must be age ≥ 50 years.

NOTE: Does not include stroke or TIA due to nonatherosclerotic causes, for example, hypertension, embolism, or hemorrhagic stroke

OR

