7.2. Method of Treatment Assignment

Patients who meet all criteria for enrollment will be randomized to 1 of the study treatment arms at Visit 3. Assignment to treatment arms will be determined by a computer-generated random sequence using an IWRS. Patients will be randomized in a 1:1:1:3 ratio to receive 5 mg LY3298176, 10 mg LY3298176, 15 mg LY3298176, or insulin glargine. The randomization will be stratified by country, baseline HbA1c concentration ($\leq 8.5\%$, $>8.5\%$ [≤ 69 , >69 mmol/mol]), and baseline SGLT-2i use (Yes or No).

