9.2.2.2. Severe, Persistent Hyperglycemia

Add-on glycemc rescue therapy will be allowed for patients who meet any of the following prespecified criteria for severe, persistent hyperglycemia. In this case, the investigator determines if a new intervention is warranted, after noncompliance with the assigned therapeutic regimen is ruled out as the reason for hyperglycemia. Patients should continue administering assigned study drugs (insulin glargine or LY3298176). The criteria are as follows:

- a) average daily BG from the QW 4-point SMBG profile >270 mg/dL (>15.0 mmol/L) over at least a consecutive 2-week period any time during the first 8 weeks post randomization;
OR
- b) average daily BG from the QW 4-point SMBG profile >240 mg/dL (>13.3 mmol/L) over a consecutive 2-week period at any time 8 to 16 weeks post randomization;
OR
- c) average daily BG from the QW 4-point SMBG profile >200 mg/dL (>11.1 mmol/L) over a consecutive 2-week period at any time beyond the first 16 weeks post randomization.
OR
- d) HbA1c $\geq 8.5\%$ (69 mmol/mol) on 2 consecutive measurements separated by at least 8 weeks at any time beyond the first 24 weeks post randomization

Investigators should first confirm that the patient is fully compliant with the assigned therapeutic regimen and that they do not have an acute condition that is raising their BG. For patients in the insulin glargine arm, the above-described criteria for severe, persistent hyperglycemia will only be applicable after Week 12. The first choice before initiating any rescue therapy for those patients during the initial 12 weeks will be to follow the TTT algorithm and to increase the dose

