10.1. Sample Size Determination

Patients will be randomized in a 1:1:1:3 ratio to 5 mg LY3298176, 10 mg LY3298176, 15 mg LY3298176, and insulin glargine to optimize CV risk assessment of LY3298176.

Although the primary objective is to establish noninferiority, sample size selection is guided by the objective of establishing superiority of each LY3298176 dose to insulin glargine relative to the reduction in mean HbA1c change from baseline at 52 weeks from randomization irrespective of adherence to investigational product or introduction of rescue therapy for persistent severe hyperglycemia (“treatment-regimen” estimand).

The sample size determination assumes that evaluation of superiority of 10 mg LY3298176 and 15 mg LY3298176 to insulin glargine will be conducted in parallel, each at a 2-sided significance level of 0.025 using a 2-sample t-test. Additionally, a 0.30% superior mean HbA1c reduction from baseline at 52 weeks from randomization for 10 mg LY3298176 and 15 mg LY3298176 compared to insulin glargine and a common standard deviation (SD) of 1.3% are assumed for statistical power calculations. Under the assumptions above, randomizing 1878 patients in a 1:1:1:3 ratio to 5 mg LY3298176 (313 patients), 10 mg LY3298176 (313 patients), 15 mg LY3298176 (313 patients), and insulin glargine (939 patients) provides 90% power to demonstrate superiority of each LY3298176 dose to insulin glargine.

The chosen sample size and randomization ratio also provides >90% power to establish superiority of 10 mg LY3298176 and 15 mg LY3298176 doses to insulin glargine in absence of confounding effects of rescue therapy for persistent severe hyperglycemia (“efficacy” estimand). For comparison of each LY3298176 dose to insulin glargine using data collected prior to the initiation of any rescue medication or premature treatment discontinuation, conducted in parallel using a 2-sample t-test, each at a 2-sided significance level of 0.025, a 0.30% superior mean HbA1c reduction compared to insulin glargine, a common SD of 1.1%, and no more than 28% initiate of any rescue antihyperglycemic medication or prematurely discontinue study drug by 52 weeks are assumed.

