For all other purposes, the primary efficacy analysis will be guided by the “efficacy” estimand defined in Section 10.3.1. This assessment will be conducted using EAS. The primary analysis model for HbA1c measurements over time will be an MMRM. The response variable of MMRM will be change in HbA1c from baseline values obtained at each scheduled postbaseline visit. The independent variables of the MMRM model are treatment group (5 mg LY3298176, 10 mg LY3298176, 15 mg LY3298176, and insulin glargine), visit, and treatment-by-visit interaction, country, SGLT-2i use (Yes or No), and baseline HbA1c as a covariate. An unstructured covariance structure will model relationship of within-patient errors. If the analysis fails to converge, the following variance-covariance matrix will be used (in order) until convergence is achieved: heterogeneous compound symmetry, compound symmetry, and first-order autoregressive. The Kenward-Roger approximation will be used to estimate denominator degrees of freedom. With the aid of the MMRM analysis, 2-sided 97.5% CI for the difference in mean change in HbA1c from baseline to 52-week visit between 10 mg LY3298176 and insulin glargine as well as between 15 mg LY3298176 and insulin glargine will be constructed. If the

upper limit of the CI is below 0.3%, LY3298176 dose will be declared noninferior to insulin glargine.

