#### 5.12.1.1. The Analysis Relative to the Efficacy Estimand

The analysis will be conducted utilizing HbA1c data in EAS from baseline through the 52-week visit with the aid of a mixed model for repeated measures (MMRM). Restricted maximum likelihood (REML) will be used to obtain model parameter estimates and Kenward-Roger option will be used to estimate denominator degrees of freedom. The response variable of the MMRM model will be the primary measure and model terms will include treatment, visit, treatment by visit interaction, country/pooled country, and SGLT2 inhibitor use at baseline as fixed effects, and baseline HbA1c as a covariate. An unstructured covariance structure will be used to model the within-patient errors. If this model fails to converge, the following covariance structures will be tested in order:

- Heterogeneous Toeplitz;
- Heterogeneous First Order Autoregressive;
- Heterogeneous Compound Symmetry;
- Toeplitz;
- First Order Autoregressive;
- Compound Symmetry.

The first covariance structure that converges will be used. Resulting Least Squares Mean (LSM) estimate of mean change from baseline in HbA1c will be plotted by visit and by study treatment.

With the aid of the MMRM analysis, 2-sided 97.5% Confidence Interval (CI) for mean change in HbA1c from baseline to 52-week visit for (10mg tirzepatide – insulin glargine) as well as for

(15mg tirzepatide – insulin glargine) will be derived. If the upper limit of the CI is  $\leq 0.3\%$ , then the respective dose of tirzepatide (10mg and/or 15mg) will be declared noninferior to insulin glargine relative to change in HbA1c from baseline.

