#### **5.12.1.2. The Analysis Relative to the Treatment-Regimen Estimand**

The analysis will be conducted utilizing HbA1c data in FAS at baseline and at the 52-week visit with the aid of an Analysis of Covariance (ANCOVA). The response variable will be the primary measure and model terms will include treatment, country/pooled country, SGLT2 inhibitor use at baseline as fixed effects, and baseline HbA1c as a covariate. The ANCOVA analysis will be conducted with multiple imputation of missing primary measure (see Section 5.12.1.3 for details) and statistical inference over multiple imputation of missing data guided by Rubin (1987).

With the aid of the ANCOVA analysis, 2-sided 97.5% CI for mean change in HbA1c from baseline to 52-week visit for (10mg tirzepatide – insulin glargine) as well as for (15mg tirzepatide – insulin glargine) will be derived. If the upper limits of the CI are  $\leq 0.3\%$ , then the respective dose of tirzepatide (10mg and/or 15mg) will be declared noninferior to insulin glargine relative to change in HbA1c from baseline.

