### **5.12.2.3. Proportion of Patients Achieving HbA1c $<7\%$ at the 52 week Visit**

The analysis relative to the “efficacy” estimand for the endpoint at 52 weeks will be conducted using EAS with missing values imputed from an MMRM model and then dichotomized. The MMRM model includes country/pooled country, SGLT2 inhibitor use at baseline, treatment, visit, and treatment-by-visit interaction as fixed effects, and baseline HbA1c as a covariate. After dichotomizing continuous HbA1c, the data is analyzed using a logistic regression model with treatment, country/pooled country, SGLT2 inhibitor use at baseline, and baseline HbA1c as a covariate. In addition, analysis will be conducted utilizing data using EAS from baseline through the 52-week visit with the aid of a longitudinal logistic regression with repeated measurements with country/pooled country, SGLT2 inhibitor use at baseline, treatment, visit, treatment-by-visit interaction as fixed effects, and baseline HbA1c as a covariate. In the case that longitudinal logistic model does not converge due to small number of events, logistic regression will be utilized to analyze proportion of patients achieving HbA1c $<7\%$  at nominal visits.

Analysis relative to “treatment-regimen” estimand will be conducted utilizing HbA1c data in FAS at baseline and at the 52-week visit with the aid of a logistic regression with multiple imputation of missing HbA1c data at the 52-week visit (see Section 5.12.1.3 for details). Model terms will include treatment, country/pooled country, SGLT2 inhibitor use at baseline as fixed effects, and baseline HbA1c as a covariate and statistical inference over multiple imputations will be guided by Rubin (1987).

[figure not shown]

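### The efficacy-estimand MMRM fits one baseline-HbA1c slope to eight visits; adding baseline-by-visit is a cheap refinement for precision, not the correction of an error

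*SAP*

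**What the plan says.** SAP 5.12.1.1 specifies treatment, visit, "treatment by visit interaction, country/pooled country, and SGLT2 inhibitor use at baseline as fixed effects, and baseline HbA1c as a covariate", with an unstructured within-patient covariance. Protocol 10.3.3.1 gives the same mean model: "visit, and treatment-by-visit interaction, country, SGLT-2i use (Yes or No), and baseline HbA1c as a covariate". Neither has a baseline-by-visit term. The HbA1c row of the Schedule of Activities gives eight post-baseline measurements up to the primary time point: Weeks 4, 8, 12, 16, 20, 24, 42 and 52.

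A model of the same form fills in missing HbA1c for one of the two efficacy-estimand analyses of HbA1c below 7% in SAP 5.12.2.3 ("treatment, visit, and treatment-by-visit interaction as fixed effects, and baseline HbA1c as a covariate"). The other is a longitudinal logistic regression, which was not evaluated here.

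The treatment-regimen analysis in SAP 5.12.1.2 works "utilizing HbA1c data in FAS at baseline and at the 52-week visit with the aid of an Analysis of Covariance", so its baseline slope is already specific to Week 52.

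Three further facts matter. Protocol 7.2 says "The randomization will be stratified by country, baseline HbA1c concentration", with a cut at 8.5%. The efficacy analysis set (EAS) drops data after rescue or after study drug is stopped (SAP Table GPGM.5.1). The efficacy-estimand power statement in Protocol 10.1 assumes that "no more than 28% initiate of any rescue antihyperglycemic medication or prematurely discontinue study drug by 52 weeks are assumed".

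**The concern.** A constant slope says that baseline HbA1c predicts the change at Week 4 as strongly as the change at Week 52. At Week 4 every tirzepatide arm has received only 2.5 mg, and glargine is at the start of weekly titration (Protocol 7.1 and 7.2.1.2). The relation could therefore differ between early and late visits.

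If it does, the baseline adjustment at Week 52 uses the wrong slope and some precision is lost. When EAS exit also depends on baseline HbA1c, the Week 52 contrast can be biased. This MMRM decides noninferiority and superiority under the efficacy estimand, which serves all purposes other than the FDA's.

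**Working it through.** **Inputs from the documents.** 313 patients per tirzepatide dose and 939 on glargine; effect 0.30; SD of change 1.1 (efficacy) and 1.3 (treatment-regimen); loss ceiling 28%; two-sided 0.025 per dose (Protocol 10.1). Screening HbA1c is 7.5 to 10.5, "at screening as determined by the central laboratory at Visit 1" (Protocol 6.1). The noninferiority margin is 0.3.

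**Assumed, because the documents do not give them.** Visit-specific slopes, correlations, exit patterns and the baseline distribution: uniform on 7.5 to 10.5 (variance 3²/12 = 0.75, SD 0.866) or truncated normal (SD 0.69).

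**1. The plan's own power.**
- Treatment-regimen: SE = 1.3 × √(1/313 + 1/939) = 0.0848; 0.30/0.0848 - 2.241 = 1.294; power 90.2%.
- Efficacy at 28% loss: SE = 1.1 × √(1/225.36 + 1/676.08) = 0.0846; 0.30/0.0846 - 2.241 = 1.304; power 90.4%.

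Both stated figures reproduce.

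**2. The fitted common slope.** With complete data it is b = (1'Σ⁻¹β)/(1'Σ⁻¹1), where β holds the visit slopes and Σ is the within-patient covariance. The weights can be negative, so b need not be an average. Across the correlation and residual-SD patterns tried, b ran from -0.47 to -0.21 for true slopes of -0.30 to -0.60, and from -0.44 to -0.01 for -0.15 to -0.65. It can lie outside the range of the true slopes.

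**3. Precision at Week 52, complete data.** Let s² be the baseline variance and σ² = 1.1² - β₅₂² s² the residual variance.
- Model-based SE ratio, common slope to baseline-by-visit: √(1 + (β₅₂ - b)² s²/σ²).
- Actual SE ratio: the same, with the added term multiplied by the share of baseline variance left within HbA1c strata. For a uniform baseline split at 8.5 the within-stratum variance is (1/3)(1/12) + (2/3)(4/12) = 0.25, so the share is 0.25/0.75 = 1/3.

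Worst cases, uniform baseline:
- Slopes -0.30 to -0.60, b = -0.21: σ² = 1.21 - 0.27 = 0.94; added term 0.39² × 0.75/0.94 = 0.121. Model-based ratio √1.121 = 1.06; actual √1.040 = 1.02.
- Slopes -0.15 to -0.65, b = -0.01: σ² = 1.21 - 0.317 = 0.893; added term 0.64² × 0.75/0.893 = 0.344. Model-based ratio √1.344 = 1.16; actual √1.115 = 1.06.

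Simulated trials of 1878 patients with stratified randomization gave actual losses of 0% to 2% and 1% to 5% on complete data, up to 6% with 28% random exit, and about 7% under other correlation assumptions. The model-based excess reached about 18% under other assumptions. With a constant slope the models tie: actual SE 0.0625 vs 0.0626, model-based 0.0632 vs 0.0632.

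At 28% random exit the common-slope 97.5% interval covered 97.1% to 98.4%. Power was 95% to 98%, against 96% to 99% with baseline-by-visit.

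**4. Bias if slopes are equal across arms at each visit.** Large simulated samples; odds of exit 1.65 to 2.7 per SD of baseline.
- Dependence in one arm only, 28% exit: about -0.05 to +0.05 (extreme 0.06).
- Equal dependence, tirzepatide vs glargine exit 10% vs 28%: -0.035 to -0.007; 28% vs 10%: +0.005 to +0.034.
- Equal dependence, 15% vs 20% or the reverse: about 0.01 at most.
- Rescue under criterion (d) of Protocol 9.2.2.2 ("on 2 consecutive measurements separated by at least 8 weeks at any time beyond the first 24 weeks post randomization"), simulated at Weeks 24 and 42: -0.009 to +0.001, or -0.012 with 5% vs 15% added random discontinuation. Read strictly, the two scheduled values beyond Week 24 are those at Weeks 42 and 52, so this criterion removes no scheduled Week 52 value.
- Baseline-by-visit: within 0.006, which is simulation noise.
- Proportion below 7% by the imputation route (true difference about 11 points): error -1.9 to +1.5 points for one-arm dependence, and -0.3 to 0.0 at 15% vs 20%.

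Wider assumed slope changes combined with strongly arm-differential exit gave more: -0.08 for -0.3 to -0.7, and -0.11 for -0.2 to -0.8.

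**5. Bias if slopes differ by arm.** Two arms, 200,000 patients, Week 52 slopes 0.2 to 0.3 apart, noise about 0.005. Baseline-by-visit left about 0.01 to 0.02 in nearly every exit scenario. At 15% vs 20% exit the common slope gave +0.004, -0.014, +0.010 and -0.020; baseline-by-visit gave +0.008, -0.011, +0.017 and -0.017. In one 28% vs 10% case baseline-by-visit was worse (-0.013 vs +0.003). It still helped when dependence was in one arm only. With equal dependence and equal 28% exit, both models were off by about 0.02.

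**The case against.** The strongest reply is that this is preference. A single baseline covariate is a complete specification, stated consistently in both documents, and the plan uses the same form for weight, other efficacy measures, safety measures and vital signs. Every size above rests on slopes and exit patterns that the documents do not contain. The one mechanism taken directly from the text, criterion (d), moves the contrast by about 0.01 against a margin of 0.3. With stratification the actual precision loss is a few percent, and power stays above plan.

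Much of this stands, and it is why the point is only a suggestion. It does not show that the added term harms precision, and uniformity with other endpoints is a weak reason to forgo a Week 52-specific slope that the treatment-regimen analysis already has.

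Two stronger readings are tempting.
- A reader might infer that noninferiority error is not controlled. Under assumed, moderately arm-differential, HbA1c-related dropout, one run gave false noninferiority rates of 0.019 and 0.030 against a nominal 0.0125 (Monte Carlo error about 0.004). The documents show neither the changing slopes nor the exit pattern that this needs.
- A reader might infer that baseline-by-visit removes the bias. That follows only if slopes are equal across arms, and the dosing rationale for changing slopes gives no reason to expect equality.

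**Conclusion.** The point holds as an optional, low-cost refinement. If the baseline slope changes over time, the common-slope model reports a Week 52 standard error up to about 6% or 16% too large under the two main slope patterns, and gives up roughly 0% to 7% of actual standard error. The overstated standard error is conservative.

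Bias is possible but small in the main scenarios: about 0.05 at most at the 28% ceiling with strongly one-sided exit, and about 0.01 at 15% vs 20%, both assuming equal slopes across arms. With arm-specific slopes, about 0.01 to 0.02 can remain under either model, even with equal exit dependence and rates, and baseline-by-visit helps only in some scenarios.

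Nothing shows a wrong analysis, a shortfall in power or a changed conclusion. The case rests on precision and on alignment with the Week 52 ANCOVA.

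**What to change.** Add baseline HbA1c-by-visit to the MMRM in SAP 5.12.1.1 and to the imputation MMRM in SAP 5.12.2.3. Keep the common-slope model as a sensitivity analysis. A matching baseline weight-by-visit term in SAP 5.12.2.2 is optional, by analogy only.

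Decide this before database lock and without results by arm, because the trial is open-label. Protocol 10.3.1 and SAP 5.2 let the SAP record a change without an amendment if no principal feature changes, and the sponsor should confirm that this is so here. The SAP already departs from the protocol on this model's fallback covariance structures (three in the protocol, six in the SAP). That is only a partial precedent, since those apply on non-convergence and this alters the mean model. State the reason as precision and alignment with the ANCOVA, not as removal of bias.

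The cost is seven parameters (eight slopes in place of one) with about 1878 patients, no new data, no loss of precision if the slope is constant, and a documented change to the stated model.

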7.2.1.2. Insulin Glargine

Dosing for patients randomized to insulin glargine will start at 10 units once daily. Patients should administer their daily doses at the time of day agreed upon between the patient and the investigator, typically before bedtime. Patients assigned to the insulin glargine treatment arm will be instructed to adjust insulin glargine doses to a target FBG of <100 mg/dL (5.6 mmol/L) based on the median value of the last 3 self-monitored fasting blood glucose (SMBG) values according to the schedule below (Riddle et al. 2003). Insulin glargine dose adjustments should occur once in a week. After Week 8, patients will continue to adjust insulin glargine per the titration algorithm; the insulin glargine dose will be also reviewed and revised, as needed, at subsequent office visits. There will be no central oversight of insulin glargine titration. Add-on

glycemic rescue therapy should be initiated for patients who met prespecified criteria for severe, persistent hyperglycemia, and further titration of glargine cannot control the condition (see [Table GPGM.4](#)).

Table GPGM.4. Titration of Insulin Glargine

Median Fasting Blood Glucose ^a		Adjustment of Insulin Glargine
mg/dL	mmol/L	
≤70	≤3.9	Decrease by 2 to 4 units ^{b,c}
71 to 99	4.0 to 5.5	No adjustment
100 to 119	5.6 to 6.6	Increase by 2 units
120 to 139	6.7 to 7.7	Increase by 4 units
140 to 179	7.8 to 9.9	Increase by 6 units
≥180	≥10.0	Increase by 8 units

Abbreviation: SMBG = self-monitored blood glucose.

^a Based on the last 3 self-monitored fasting blood glucose (SMBG) values.

^b Dose should also be decreased by 2 to 4 units in the following situations:

- If multiple episodes of nonsevere hypoglycemia were recorded during the assessment period at any time during the day; and/or
- If at least 1 episode that met the criteria for severe hypoglycemia (events requiring assistance to administer therapy) or was associated with self-monitored blood glucose (SMBG) value <54 mg/dL (<3.0 mmol/L) was recorded during the assessment period.

^c If only 1 hypoglycemic episode with SMBG value ≥54 mg/dL (≥3.0 mmol/L) and ≤70 mg/dL (≤3.9 mmol/L) was recorded, insulin dose should not be changed.

Source: Riddle et al. 2003.

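### The confirmatory ANCOVA and MMRM pool one variance over all four arms, so the standard errors against glargine are moderately wrong, in an unpredictable direction, if spread differs by arm

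*SAP*

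**What the plan says.** SAP 5.12.1.1 (efficacy estimand) fits one MMRM to all arms by REML with Kenward-Roger degrees of freedom: "An unstructured covariance structure will be used to model the within-patient errors". Its fallback list includes heterogeneous structures, but these let the variance differ between visits, not between arms. Kenward-Roger does not relax a common covariance either.

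SAP 5.12.1.2 (treatment-regimen estimand) fits one ANCOVA: "The response variable will be the primary measure and model terms will include treatment, country/pooled country, SGLT2 inhibitor use at baseline as fixed effects", plus baseline HbA1c. The results are combined over imputations by Rubin's rules, so the within-imputation variance comes from that ANCOVA. SAP 5.12.2.2 applies both models to body weight, with changed covariates.

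Neither the SAP nor Protocol 10.3 mentions an arm-specific variance, a robust variance or an unequal-variance sensitivity analysis. The SAP does not say in words that the variance is common. That is the ordinary reading of these specifications, and no alternative is given.

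Protocol 10.1 sets the allocation: "Patients will be randomized in a 1:1:1:3 ratio to 5 mg LY3298176, 10 mg LY3298176, 15 mg LY3298176, and insulin glargine". The only variance information in the documents is in the same section and is common to all arms: "a common standard deviation (SD) of 1.3% are assumed for statistical power calculations", with 1.1% for the efficacy estimand.

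**The concern.** A pooled residual variance is an average over the whole trial. The sampling variance of one contrast depends only on the two arms compared, weighted by the inverse of their sizes. The two agree when all arms have the same spread and generally disagree otherwise.

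Here glargine has 939 of 1878 patients and so supplies half of the pooled variance. In a contrast of 313 against 939 with equal spread, however, the tirzepatide arm supplies three-quarters of the sampling variance.

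The two-sided 97.5% intervals decide noninferiority for 10 mg and 15 mg, and the p-values from the same models drive the testing sequence in SAP 5.12.3. That sequence controls the overall 5% level only if each test holds its own level. The mismatch depends on a ratio of variances, so it does not shrink as the sample grows.

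**Working it through.** **Inputs.** From Protocol 10.1: 313 patients per tirzepatide dose and 939 on glargine; difference 0.30%; SD 1.3%; two-sided 0.025 for each of 10 mg and 15 mg (critical value 2.2414). Assumed, because the documents give no arm-specific SD: the ratio r of tirzepatide to glargine variance, from 0.5 to 2.0, equal across the three doses. The calculation uses complete data and no covariates.

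**Step 1: the plan's own figure.** Protocol 10.1 states "15 mg LY3298176 (313 patients), and insulin glargine (939 patients) provides 90% power to demonstrate superiority", for "a 0.30% superior mean HbA1c reduction from baseline at 52 weeks from randomization" tested "each at a 2-sided significance level of 0.025 using a 2-sample t-test". The standard error is 1.3 × sqrt(1/313 + 1/939) = 0.0848, and power = Phi(0.30/0.0848 − 2.2414) = 90.2%. The stated 90% reproduces. The interval half-width is 2.2414 × 0.0848 = 0.190 percentage points.

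**Step 2: model against true variance.** Take the glargine variance as 1 and each tirzepatide variance as r.

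- Model: [(r + 1)/2] × (1/313 + 1/939) = 2(r + 1)/939
- True: r/313 + 1/939 = (3r + 1)/939
- SE true/model = sqrt[(3r + 1)/(2(r + 1))]
- True two-sided level = 2 × [1 − Phi(2.2414 ÷ (SE true/model))]; the one-sided noninferiority error is half of this

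| r | SE true/model | Model SE | Two-sided level (nominal 0.025) | One-sided error (nominal 0.0125) |
|---|---|---|---|---|
| 0.5 | 0.913 | 9.5% too large | 0.014 | 0.0070 |
| 0.7 | 0.955 | 4.7% too large | 0.019 | 0.0095 |
| 1.0 | 1.000 | right | 0.025 | 0.0125 |
| 1.5 | 1.049 | 4.7% too small | 0.033 | 0.0163 |
| 2.0 | 1.080 | 7.4% too small | 0.038 | 0.0190 |

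For r = 2.0: (3 × 2 + 1)/(2 × 3) = 7/6, with square root 1.080; 2.2414/1.080 = 2.075, which gives 0.019 in one tail. Simulation with 2,000,000 trials per ratio gives one-sided errors of 0.0070 at r = 0.5 and 0.0190 at r = 2.0. Where SAP 5.12.3 tests at two-sided 0.05, replacing 2.2414 by 1.960 gives a range of 0.032 to 0.070. The results depend only on r, so they apply to body weight for the same r.

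**Step 3: is the allocation the cause?** With four equal arms and the same four-arm pooling, the model variance is proportional to 2 × (3r + 1)/4 and the true variance to r + 1. SE true/model becomes sqrt[2(r + 1)/(3r + 1)], the exact reciprocal of the ratio in Step 2. The two-sided levels are 0.041, 0.032, 0.019 and 0.015 for r = 0.5, 0.7, 1.5 and 2.0. The error is of similar size and opposite sign.

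**Step 4: does the remedy work?** With arm-specific variances in the contrast, simulated one-sided error is 0.0126 to 0.0128 for SD ratios from 0.67 to 1.5 (variance ratios 0.45 to 2.25). Power at equal SDs stays at 90.2%.

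**The case against.** The case against runs as follows. A pooled-residual ANCOVA and an unstructured MMRM with Kenward-Roger are conventional, and protocol and SAP agree on them. Nothing in the documents shows unequal spread; the only variance statements are common SDs. The effect is modest, and if glargine is the more variable arm the tests are conservative.

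Most of this stands. It limits the point without removing it, because the common SD is a planning assumption and does not justify the analysis variance. Three stronger readings are tempting, and the documents do not support them.

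- **That 1:1:1:3 allocation is to blame.** Step 3 shows that four equal arms would also be off. The cause is pooling over arms that may differ.
- **That the arms are unlike by design, so tirzepatide must be more variable.** Protocol 7.2.1.2 titrates glargine to a fasting glucose target, and Protocol 7.7.1 permits dose reduction of tirzepatide. But 7.2.1.2 also says that titration has no central oversight, and a fasting glucose target says nothing about spread in body weight. Neither direction can be inferred.
- **That the weight analyses are badly inflated.** Any such figure needs weight SDs by arm, and the documents give none.

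The complete-data calculation is also a simplification. Dropout alters the MMRM weights. In the ANCOVA, the between-imputation part of the variance comes from same-arm imputation (SAP 5.12.1.3) and is not pooled in this way. The exact figures would change.

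**Conclusion.** The point holds as a conditional one. If the true variance ratio lies between 0.5 and 2.0, the pooled models give a standard error between 9.5% too large and 7.4% too small. The two-sided level is then 0.014 to 0.038 against 0.025, and the one-sided noninferiority error 0.007 to 0.019 against 0.0125. Intervals are too narrow only if tirzepatide is the more variable group. If glargine is, they are too wide and power is lost.

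This rests on the assumed range for r, equal spread across the three doses, complete data, and reading the silent specification as a common variance. Unequal spread among the doses would change the figures dose by dose.

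A reader might infer that the type 1 error is inflated or the sample size wrong. Neither follows: the direction is unknown, and the 90% power reproduces under its stated common SD. The plan contains no demonstrated error here. Its confirmatory interval widths rest on an unstated and unchecked assumption that can be dropped cheaply.

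**What to change.** **ANCOVA (SAP 5.12.1.2, and 5.12.2.2 for weight).** Use heteroscedasticity-consistent standard errors within each imputed data set, then combine by Rubin's rules. This is a one-option change with almost no loss of power when the variances are equal.

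**MMRM (SAP 5.12.1.1, and 5.12.2.2 for weight).** Choose one of two:

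- Keep the existing unstructured covariance and use empirical (sandwich) standard errors. These replace the Kenward-Roger adjustment, a negligible loss with 313 or more patients per arm.
- Fit a treatment-specific unstructured covariance, with a stated fallback to the pooled matrix plus sandwich standard errors if it does not converge. The cost is not trivial. The Schedule of Activities shows eight post-baseline HbA1c visits to Week 52 (Weeks 4, 8, 12, 16, 20, 24, 42 and 52), so one matrix has 8 × 9/2 = 36 parameters. Four matrices have 144, which is 108 more, with some risk of non-convergence. Without the stated fallback, non-convergence would lead into the SAP's list of more restrictive structures.

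If the sponsor prefers to keep the pooled models as primary, the minimum is to pre-specify one of these as a sensitivity analysis and to report residual SDs by arm.
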